Appendix A: Definitions

A. Surgical site infections

Surgical site infection is defined at 30 days post-surgery using the Centers for Disease Control (CDC) definition of deep incisional or superficial incisional SSI as follows

- 1. The infection must occur within 30 days of the index operation
- 2. The infection must involve the skin, subcutaneous, muscular, or fascial layers of the incision
- 3. The patient must have at least one of the following: purulent drainage from the wound; organisms detected by wound swab; diagnosed clinically or at imaging; wound opened spontaneously or by a clinician
- 4. The patient has at least one of the following: pain, tenderness, localized swelling, redness, heat at the wound site, systemic fever (>38°C).

B. Clavien-Dindo Complications

Adverse post-operative events may be classified in different ways:

- Failure of treatment This occurs when the original surgery fails to achieve its intended benefits; for example, persistent pain following laparoscopic cholecystectomy or tumour recurrence following cancer surgery.
- Sequelae: The recognised consequences of a given procedure; for example, gut
 malabsorption following a large small bowel resection or immune deficiency following
 splenectomy.
- **Complication**: Any deviation from the normal post-operative course that has an adverse effect on the patient and is not either a treatment failure or sequel.

In the Clavien-Dindo classification ³⁵, the factor determining the severity of a complication is the treatment required. Consequently, a given complication may be graded differently depending on how it has been managed. For example, an anastomotic leak may be managed just with antibiotics if it is contained (grade II) or it may require re-operation under anaesthetic (grade IIIb).

Some other considerations:

- Intra-operative complications are not considered unless they have an adverse effect on the patient post-operatively. The only exception to this is intra-operative death; this is classified as grade V.
- All post-operative adverse events are included, even when there is no direct relationship to the surgery.
- All adverse events within the follow-up period (30 days) are included, even after following discharge.
- Diagnostic procedures are not included. For example, a diagnostic
 oesophagoduodenoscopy (OGD) to look for a source of bleeding without any
 intervention would not be considered a complication, but a therapeutic OGD with clipping
 of a bleeding vessel would be considered a grade IIIa complication. Since negative
 exploratory laparotomies are considered diagnostic procedures, they should not be
 recorded as complications.

Grade	Definition (examples listed in italics)
I	Any deviation from the normal postoperative course without the need for pharmacological (other than "allowed therapeutic regimens"), surgical, endoscopic or radiological intervention.
	Allowed therapeutic regimens are: selected drugs (antiemetics, antipyretics, analgesics, diuretics and electrolyte
	replacement), physiotherapy and wound infections opened at the bedside but not treated with antibiotics.
	Examples : Ileus (deviation from the norm); hypokalaemia treated with K; nausea treated with cyclizine; acute kidney injury treated with intravenous fluids.
П	Requiring pharmacological treatment with drugs beyond those allowed for
	grade I complications. Blood transfusions and total parenteral nutrition are also included.
	Examples : Surgical site infection treated with antibiotics; myocardial infarction treated medically; deep venous thrombosis treated with enoxaparin; pneumonia or urinary tract infection treated with antibiotics; blood transfusion for anaemia.
Illa	Requiring surgical, endoscopic or radiological intervention, not under general
	Anaesthetic (GA).
	Examples: Therapeutic endoscopic therapy (do not include diagnostic procedures); interventional radiology procedures.
IIIb	Requiring surgical, endoscopic or radiological intervention, under GA.
	Examples: Return to theatre for any reason.
IVa	Life-threatening complications requiring critical care management with single organ dysfunction, or neurological
	complications including brain haemorrhage and ischemic stroke (excluding TIA).
	Examples : Single organ dysfunction requiring critical care management, e.g. pneumonia with ventilator support, renal failure with filtration; SAH; stroke
IVb	Life-threatening complications requiring critical care management with multi-organ dysfunction.

C. Clinical Frailty Score

Clinical Frailty Scale

1 Very Fit – People who are robust, active, energetic and motivated. These people commonly exercise regularly. They are among the fittest for their age.

7 Severely Frail – Completely dependent for personal care, from whatever cause (physical or cognitive). Even so, they seem stable and not at high risk of dying (within ~ 6 months).

2 Well - People who have no active disease symptoms but are less fit than category 1. Often, they exercise or are very active occasionally, e.g. seasonally.

8 Very Severely Frail – Completely dependent, approaching the end of life. Typically, they could not recover even from a minor illness.

3 Managing Well - People whose medical problems are well controlled, but are not regularly active beyond routine walking.

9 Terminally III – Approaching the end of life. This category applies to people with a life expectancy <6 months, who are not otherwise evidently frail.

4 Vulnerable – While not dependent on others for daily help, often symptoms limit activities. A common complaint is being "slowed up", and/or being tired during the day.

5 Mildly Frail – These people often have more evident slowing, and need help in high order IADLs (finances, transportation, heavy housework, medications). Typically, mild frailty progressively impairs shopping and walking outside alone, meal preparation and housework.

6 Moderately Frail – People need help with all outside activities and with keeping house. Inside, they often have problems with stairs and need help with bathing and might need minimal assistance (cuing, standby) with dressing.

Scoring frailty in people with dementia

The degree of frailty corresponds to the degree of dementia. Common **symptoms in mild dementia** include forgetting the details of a recent event, though still remembering the event itself, repeating the same question/story and social withdrawal.

In moderate dementia, recent memory is very impaired, even though they seemingly can remember their past life events well. They can do personal care with prompting.

In severe dementia, they cannot do personal care without help.

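### The only Clavien-Dindo grade IIIb example conflicts with the appendix's rule on diagnostic procedures and blurs its IIIa/IIIb split by general anaesthesia, so some returns to theatre may be graded too high or inconsistently

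*Protocol*

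**What the plan says.** Protocol section 8 lists 30-day Clavien-Dindo complications as a secondary outcome and refers to Appendix A for definitions. Part B of that appendix contains the following.

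- **Grading principle:** "the factor determining the severity of a complication is the treatment required".
- **Grade IIIa definition:** "Requiring surgical, endoscopic or radiological intervention, not under general" anaesthetic. Its examples are "Therapeutic endoscopic therapy (do not include diagnostic procedures); interventional radiology procedures".
- **Grade IIIb definition:** "Requiring surgical, endoscopic or radiological intervention, under GA". Its only example is "Return to theatre for any reason".
- **Diagnostic rule:** "Diagnostic procedures are not included". The same bullet applies this to surgery: negative "exploratory laparotomies are considered diagnostic procedures, they should not be" recorded as complications.
- **Narrative example above the table:** on an anastomotic leak, "it may require re-operation under anaesthetic (grade IIIb"). The word general does not appear there.

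**The concern.** An example in a grading table is there to settle doubtful cases. This one has no limit on purpose and names no anaesthetic, while the rules around it depend on exactly those two features. A data collector with a negative re-exploration, or with a wound explored under spinal or local anaesthesia, can find support in the appendix for two different answers.

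Section 10 anticipates more than 1000 centres, and section 12 allows teams that include medical students. Common wording is a main safeguard for consistent grading. Errors would be hard to correct later: under section 9 the database is irrevocably de-identified, and each site destroys its patient log once data collection ends.

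**Working it through.** The protocol gives no figure to reproduce on this point, so the check is mainly a comparison of texts.

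**Step 1. Classify each kind of return to theatre by rule and by example** (none involving organ dysfunction or death).

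| Event | Definitions and diagnostic rule | IIIb example, read literally | Agree? |
|---|---|---|---|
| Therapeutic, under GA | IIIb | IIIb | Yes |
| Therapeutic, not under GA | IIIa | IIIb | No |
| Negative or purely diagnostic, under GA | Not recorded | IIIb | No |
| Negative or purely diagnostic, not under GA | Not recorded | IIIb | No |

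Every disagreement runs upward. The first row, the therapeutic return under GA, is graded correctly either way.

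**Step 2. Does placing the example in its row remove the conflict?** The example stands under a definition that requires GA. If that condition is carried into the example, the second and fourth rows no longer match it. The third row still does, because the example admits every reason and a negative exploration under GA meets both the condition and the example. The conflict with the diagnostic rule therefore survives the more generous reading.

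**Step 3. Does nearby text favour the generous reading?** Two items pull against it. The IIIa examples cover endoscopy and interventional radiology only, so no surgical return is ever shown as IIIa. The narrative example attaches IIIb to re-operation under anaesthetic without saying general. The IIIa examples do carry a reminder to leave out diagnostic procedures; the IIIb row carries none.

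**Step 4. Illustration of scale.** The sample of about 5,000 patients is from section 10. The documents give no reoperation rate and no share of returns that are non-GA or diagnostic; the ranges below are assumptions.

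- Returns to theatre = patients × 30-day return rate: 5,000 × 0.5% = 25, up to 5,000 × 3% = 150.
- Exposed returns = returns × share non-GA or purely diagnostic: 25 × 10% = 2.5 (about 3), up to 150 × 50% = 75.
- As a share of the cohort: 2.5 / 5,000 = 0.05%, up to 75 / 5,000 = 1.5%.

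These are ceilings for each set of assumptions, because they suppose that every collector follows the example over the definition.

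**Step 5. What moves.** An anaesthesia misgrade shifts an event from IIIa to IIIb and leaves the grade III total and the any-complication count unchanged. A negative exploration recorded as IIIb adds an event to the grade III total, and to the any-complication count if the patient has no other complication.

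**The case against.** The strongest reply is that the table presents its examples as illustrations of a definition, and the IIIb definition requires GA. On this view the example's wording concerns the indication, not the anaesthetic, and the anaesthesia conflict disappears. The diagnostic rule is stated just before the table and decides whether an event is a complication at all; the table only grades events that have passed that test. Each team also has a specialist consultant, and the Data Summary Document and REDCap fields, which are not available here, may already clarify the point.

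Much of this stands. The anaesthesia conflict can be read away, so that part is an ambiguity and not a flat contradiction. The argument about the diagnostic rule tells a careful reader which text should prevail, but it does not make the example consistent with the rule.

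A reader might also infer several stronger things that the documents do not support:

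- **That reoperations will be systematically over-graded.** Only non-GA or purely diagnostic returns are exposed, and nothing shows how collectors will resolve the conflict.
- **That the error differs by surgical technique or operator type.** Nothing links the anaesthetic used at reoperation to either.
- **That a planned second-side repair would count as IIIb.** Appendix A defines a complication as an adverse deviation from the normal postoperative course, which a planned stage is not.
- **That the 30-day reoperation rate is distorted.** Section 8 lists it separately, and it does not depend on this grade.

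**Conclusion.** The point holds in a limited form. As written, the IIIb example contradicts the rule that diagnostic procedures and negative exploratory laparotomies are not recorded. It also fits poorly with the IIIa/IIIb split by GA, given the missing surgical example in IIIa and the unqualified reference to anaesthetic in the narrative. Some returns to theatre may be graded too high, and centres may grade identical events differently.

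The size cannot be determined from the protocol. The range of about 3 to 75 patients rests on the assumed rates and on full adherence to the example, and shows only how weakly the number is constrained. The effect is confined to the secondary Clavien-Dindo outcome; the primary outcome, compliance with the audit standards, is untouched. This is a worthwhile wording correction, not a threat to the study's main result.

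**What to change.** Reconcile the three places in Appendix A, part B, with the appendix's own definitions:

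1. Change the IIIb example to: *therapeutic return to theatre under GA (excluding diagnostic procedures and negative explorations)*.
2. Add to the IIIa examples: *therapeutic return to theatre not under GA*.
3. In the narrative on anastomotic leak, specify *general* anaesthetic for grade IIIb.

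Check any matching help text in the Data Summary Document and REDCap for the same wording. The cost is three short text edits, with no additional patients, data fields or analysis. No change to the 30-day reoperation outcome is needed.

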Appendix B: Steps for successful inclusion of your centre

- 1. Contact your hospital lead about participation in the HIPPO study to register a mini-team.
- 2. Form a mini-team of up to five collaborators, that can either be medical students, junior doctors, trainees or consultants.
- 3. Each team can cover as many periods as they want to, working together to deliver 30-day follow-up. Discuss with your regional lead to establish a 28-day consecutive data collection period from below to suit your availability:
 - Period 1: 00:00 30th Jan 2023 23:59 26th Feb 2023 (+ 30 Day Follow-up)
 - Period 2: 00:00 27th Feb 2023 23:59 26th Mar 2023 (+ 30 Day Follow-up)
 - Period 3: 00:00 27th Mar 2023 23:59 23th Apr 2023 (+ 30 Day Follow-up)
 - Period 4: 00:00 24th April 2023 23:59 21st May 2023 (+ 30 Day Follow-up)
- 4. Ensure that you secure authorisation from your hospital's Research Governance Office (RGO) prior to commencing data collection. This may seem daunting at first but is in fact quite straight forward. Every hospital has a RGO and it is a simple case of approaching them with the information we have prepared in this protocol and applying for authorisation . You will need a local consultant to support you and sign the application form (this should be the same consultant which is supervising the mini- teams). Ensure that the audit department knows that this is part of a national project and that you will enter data on REDCap.

It is essential that you begin this process **immediately**; approval can take up to a month or more. You may have to contact or even visit the hospital before your placement starts to ensure that you will be ready. If you have any difficulties contact your hospital lead, national lead or the steering committee.

- 5. Contact your hospital's RGO to request permission to submit data to REDCap.
- 6. Agree with your RGO on how you will facilitate 30-day follow-

up. You will require the hospital number for each patient to undertake follow-up, and so this needs to be stored in a safe and secure manner until accessed for 30-day follow-up, in line with local and national data governance guidance.

- 7. Once the study is authorised and you have Human Research Ethics Approval (HREC), please forward evidence of this to your regional lead. REDCap accounts will not be issued until proof of RGO authorisation AND HREC approval has been received.
- 8. Arrange to meet with the other members of your mini-team, including the junior doctor and, if possible, supervising consultant. If possible, it is also highly recommended to meet with the preceding mini-team at your centre:
 - They will have a lot of helpful advice regarding what worked well. In your mini-team, agree in advance who will be responsible for each stage of the project (e.g. identifying patients, collecting baseline data, completing follow-up, data entry to REDCap).
 - Talk through how you will identify patients and collect required data.
- Identify all patients fitting the inclusion criteria within your specified four-week window.
 Contact your regional lead with any questions or issues that may arise over your data collection period.
- 10. Regularly follow-up for information on complications over the 30-day post-operative period. This study is prospective, so you should not wait until the end of the post-operative period to follow-up patients (this would be retrospective). Discuss the best way to follow up patients with the hospital lead, because this might vary from centre to centre.

Be proactive in identifying post-operative adverse events, as this will prevent underestimation of true complication rates. Remember that in this audit no changes to normal patient follow-up should be made.

Strategies for identifying complications in the follow-up period include:

- Regularly reviewing patient notes to identify in-hospital complications.
- Reviewing clinic notes and clinic letters, if seen in clinic by 30 days.
- Checking electronic systems and handover lists for re-admissions.

Checking for A&E re-attendances.

If case notes are reviewed shortly prior to discharge they do not be need to be requested/retrieved again for follow-up at 30-days, but do check electronic records for discharge letters, clinic letters, re-admissions.

- 11. Ensure all data has been uploaded to the REDCap system by the data collection deadline, and you have completed all fields, avoiding missing data points. If more than 5% of patients at your centre have missing data, your centre cannot be included in the HIPPO dataset and your name will be withdrawn from the author list.
- 12. It is a condition of participation in HIPPO that following completion of the audit at your centre you must ensure that your local results are presented to your hospital's surgical department and/or reported back to the audit department. You may also like to return to present again at a later date, when the final national results of HIPPO become available

